- a) **Specific Aim 1: Collect preliminary data on the psychiatric outcomes of pregnant women with Bipolar Disorder who undergo a TDM protocol for lamotrigine.** Hypothesis: Women undergoing a TDM protocol for lamotrigine will have a low rate (defined as <30%) of psychiatric relapse. Psychiatric outcomes will be defined by clinician interview, the Edinburgh Postnatal Rating Scale (EPDS) and the Young Mania Rating Scale (YMRS).
- b) **Specific Aim 2: Collect adverse event data from pregnant women with Bipolar Disorder undergoing a TDM protocol for lamotrigine.** Adverse event data will be collected using the UKU side effect semi-structured interview and the Frequency, Intensity, and Burden of Side Effects Rating (FIBSER) scale.
- c) **Specific Aim 3: Collect preliminary data on the obstetrical outcomes of pregnant women with Bipolar Disorder who undergo a TDM protocol for lamotrigine.** Obstetrical outcomes will be defined by review of the delivery admission chart by an obstetrician using the Peripartum Events Scale (PES).
- d) **Specific Aim 4: Collect preliminary data on infant outcomes whose mothers underwent a TDM protocol for lamotrigine.** Pediatric outcomes will be defined by review of the infant delivery chart by a pediatrician and by a neurobehavioral assessment using the Neonatal Intensive Care Unit (NICU) Network Behavioral Scale (NNS).

3. Background:

Evidence indicates that serum levels of lamotrigine decrease by 200-250% across pregnancy¹⁹, and that the clearance of lamotrigine can be increased 10-fold across pregnancy in many but not all women²⁰. In the epilepsy literature, levels between 2.5 and 15 have been reported for therapeutic efficacy with higher levels correlated with increasing signs of toxicity²¹. In the epilepsy literature, there is a published protocol for lamotrigine management before, during, and after pregnancy²² for seizure control as follows:

- *Prior to pregnancy, adjust lamotrigine dose to minimum effective dose to attain clinical stability. Obtain a reference concentration (RC), preferably when the patient is not taking oral contraceptives.*
- *During pregnancy, monitor lamotrigine concentration every 4 weeks. If serum concentration falls below RC, increase lamotrigine dose by 20-25% and re-measure serum level after 4 additional weeks. If serum level does not fall below RC, maintain same dose but check level again in four weeks.*

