Our primary hypothesis is that prophylactic TDM for lamotrigine will result in a lower than expected rate of psychiatric relapse. The study will be an unblinded pilot study testing a TDM protocol for lamotrigine and will examine psychiatric, adverse event, obstetrical and infant outcomes. Because this is a pilot study we have chosen not to recruit a comparison group of women and instead focus on collecting outcomes for a larger sample of women who will undergo TDM for lamotrigine. Based on the literature we would expect the relapse rate in women who are maintained on their pre-pregnancy lamotrigine dosage to be at least 30%^{1,2}. Although our study design will not demonstrate superiority, it will provide preliminary evidence of efficacy and safety data for both the participant and her infant and will be the largest study examining a specific approach to managing lamotrigine during pregnancy in patients with Bipolar Disorder. We hope these data will then serve as a basis for a multisite randomized trial of prophylactic TDM for lamotrigine compared to treatment as usual in the future.

Pregnant women with Bipolar Disorder who are taking lamotrigine will be evaluated monthly during pregnancy including a clinical evaluation and a blood draw for lamotrigine levels at each visit. Based on the TDM protocol described below their lamotrigine dosing will be adjusted as needed based on their blood levels compared to the RC that was obtained prior to pregnancy or early in pregnancy while clinically stable. After delivery women and their infants will be assessed at 1, 2, 4, and 6 weeks postpartum.

Sample Size. We will recruit and follow up to 20 women with Bipolar Disorder who have chosen to take lamotrigine during pregnancy with a goal of maintaining a sample size of 16 allowing 4 drop-outs.

Recruitment. Participants will primarily be recruited through the Johns Hopkins Women's Mood Disorders Center (WMDC) and through referrals from the Obstetrics department. We will advertise on the WMDC Facebook site, the WMDC research site, EPIC and in local publications.

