- e. **Justification for inclusion of a placebo or non-treatment group.** There will be no placebo or non-treatment group.

- f. **Definition of treatment failure or participant removal criteria.** Participants will be removed from the study if they meet criteria for Relapse as described above. Participants will also be removed if they are lost to follow-up or are noncompliant with the study protocol.
- g. **Description of what happens to participants receiving therapy when study ends or if a participant's participation in the study ends prematurely.** Participants will return for clinical care to their outpatient provider at the end of the study or if their participation ends prematurely.

5. Inclusion/Exclusion Criteria

Inclusion Criteria. Pregnant women with a history of Bipolar Disorder (Bipolar Disorder I, Bipolar Disorder II or Bipolar Disorder not otherwise specified) who are taking lamotrigine and who intend to continue lamotrigine through pregnancy will be enrolled. All participants must be in the first 20 weeks of pregnancy at the time of enrollment. All participants must also be on stable doses of lamotrigine (for the past 4 weeks), have an EPDS <13, a YMRS <12 and be judged by the study clinician to be clinically stable. Participants may be taking other psychiatric and nonpsychiatric medications.

Exclusion Criteria. Participants who have active suicidal ideation or who are clinically unstable will be excluded. Participants who are dependent on alcohol, marijuana or other substances in the 90 days prior to study entry will be excluded.

6. Drugs/ Substances/ Devices

- a. **The rationale for choosing the drug and dose or for choosing the device to be used.** Lamotrigine is an evidence-based treatment for Bipolar Disorder in pregnancy. The rationale for our TDM/dosing regimen is based on recommendations in the epilepsy literature. There is currently no established protocol for the dosing of these drugs in pregnant patients with Bipolar Disorder.
- b. **Justification and safety information if FDA approved drugs will be administered for non-FDA approved indications or if doses or routes of administration or participant populations are changed.** There are no drugs with FDA approval for the management of mood disorders in pregnancy. Therefore, we must use FDA approved drugs for non-FDA approved indications, a common clinical practice.

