- c. **Justification and safety information if non-FDA approved drugs without an IND will be administered.** Not applicable.

7. Study Statistics.

We will perform descriptive statistics that include percent tabulations for categorical variables, means with standard deviations for continuous variables, and medians with ranges where more appropriate. The primary endpoint is the proportion of women who experience psychiatric relapse from the time of enrollment to 6 weeks postpartum. Relapse will be defined as one of the following: meeting SCID criteria for a Major Depressive Episode, meeting SCID criteria for a hypomanic or manic episode, development of high risk suicidal plan or attempt, or psychiatric hospitalization. We do not have a comparison group but would normally expect a relapse rate of approximately 30% based on the literature We will also collect and describe adverse events, obstetrical and infant outcomes.

8. Risks.

a) **Medical Risks.** The risks and discomforts are expected to be minimal and rare. During interviews, the participants may experience some discomfort or anxiety because of the personal nature of the questions. There may be some risk that the research participant may find the diagnostic interview uncomfortable or feel it is an invasion of privacy. Venipuncture may be associated with the momentary discomfort of the needle stick, fainting, bruising and rarely infection. There is also a risk for loss of confidentiality. Other risks include maternal side effects or toxicity from lamotrigine, infant side effects or toxicity from lamotrigine, and maternal psychiatric relapse.

b) **Steps Taken to Minimize Risks:**

Interviews, Questionnaires: A trained research assistant will be available at all times while the participant is filling out questionnaires. The Principal Investigator will also be available by telephone, and WMDC clinicians (including a psychiatrist) will be onsite during the administration as well. Should the participant become distressed, the study staff member can provide reassurance and evaluate her psychiatric state. Participants will be informed during screening and consenting procedures that they do not have to answer or complete tasks that cause them distress. Each participant will be directed to inform the study team member if she wishes to skip a certain part. If the study staff member determines that the participant is experiencing a psychiatric emergency, the steps listed below under that heading will be taken.

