Blood draw: In order to decrease the risks associated with venipuncture, we will employ staff that is experienced in blood drawing procedures.

Psychiatric Urgency/Emergency: Management of Psychiatric Urgency/Emergency: In order to minimize the risk of suicide, we will follow the following procedures for protection against this risk:

- Each participant will be asked directly at every visit whether or not they are having thoughts about harming themselves or anyone else, including their child/children. All study personnel have (or will have) experience in interviewing participants with psychiatric disorders and will have been trained how to handle reports of suicidal ideation or threats of harm to others – including when to call 911 or campus security.
- The study psychiatrists will be available by pager to the participants and the research assistants during the study.
- An emergency contact information sheet will be maintained at each clinical site on each participant including telephone contacts, an emergency contact person, the participant's psychiatric outpatient treatment provider's name and contact information and the participant's home address as well as contact information for the participant's obstetrician and the infant's pediatrician. This will provide important information in case of psychiatric or medical urgency/emergency. All participants will sign a release of information form in order to allow study personnel to contact their emergency contact and/or providers if necessary during the study.
- If a participant who reports suicidal or otherwise harmful thoughts (to themselves or others) is judged to be at risk by the study psychiatrist, they will be taken to the Emergency Room/Emergency Mental Health. The Emergency Room is on the same campus as the study sites. If the participant is interviewed by phone and is judged to be at risk, the participant will be instructed to go to the emergency room and if there is a question regarding

compliance with this request the study psychiatrist will call 911 as well as the emergency contact information maintained for each participant. If the participant is interviewed by phone and is judged to be at imminent risk of suicide, the study psychiatrist will call 911 and have the police complete a welfare check.

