Additional Protections for Pregnant Women, Human Fetuses and Neonates. This study meets all requirements for research in this vulnerable population as described by DHHS regulations and OHRP guidance. This study is essentially an observational study with blood and clinical data collection only and no active study intervention that increases the risk beyond what the woman and her child would face outside of participation in the study.

9. Benefits

Participants will be paid for their time and will undergo more regular psychiatric evaluation than is standard for most psychiatric patients. Participants may avoid psychiatric relapse by participating in the study due to the increased monitoring of lamotrigine blood levels and adjustment of lamotrigine dosing.

Developing more effective management strategies for bipolar disorder during pregnancy will allow us to decrease the associated maternal and infant morbidity and mortality by working towards decreasing the relapse rate during the perinatal time-period.

10. **Payment and Remuneration. Detail compensation for participants including possible total compensation, proposed bonus, and any proposed reductions or penalties for not completing the protocol.** Participants will be compensated for parking or taxi service for their visits. In addition, they will receive compensation up to the amount of \$450 if they complete the entire study. If the participant fails to complete all visits, they will be paid based on the visits spent in the study: Participants will be paid \$25 for each pregnancy visit completed and \$75 for each postpartum visit. If participants opt for a home visit postpartum, they will receive \$50 instead. Participants will also be paid a bonus of \$100 for achieving a minimum of 5 pregnancy visits and 2 postpartum visits in order to encourage continuity of participation. Lab costs for lamotrigine levels will be covered by the study as well. If acute medical care or medical or psychiatric hospitalization is required during the course of the study, the individual participant and/or their health insurance will be expected to cover those costs.

11. Costs

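### Section 4f removes noncompliant women and nothing provides for learning their relapse status afterwards: an avoidable but modest loss of primary outcome data

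*Protocol*

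**What the plan says.** The endpoint is given in Section 4a (Data Collection, item a) and again in Section 7: "The primary endpoint is the proportion of women who experience psychiatric relapse from the time of enrollment to 6 weeks postpartum". Relapse means meeting SCID criteria for a depressive, hypomanic or manic episode, a high-risk suicidal plan or attempt, or psychiatric hospitalization. Specific Aim 1 in Section 2 sets the reference value: "Women undergoing a TDM protocol for lamotrigine will have a low rate (defined as <30%) of psychiatric relapse".

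Section 4f lists the grounds for removal. Relapse is one. The others are: "Participants will also be removed if they are lost to follow-up or are noncompliant with the study protocol". Noncompliance is not defined. Section 4g then says: "Participants will return for clinical care to their outpatient provider at the end of the study or if their participation ends prematurely".

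Section 4a (Sample Size) plans for up to 20 women "with a goal of maintaining a sample size of 16 allowing 4 drop-outs", without dividing the drop-outs by cause. Section 10 foresees incomplete attendance: "If the participant fails to complete all visits, they will be paid based on the visits spent in the study". It does not say whether missed visits count as noncompliance.

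**The concern.** A woman can depart from the study protocol and still be willing to say how she is. Section 4f makes no such distinction: noncompliance ends participation, and nothing in the Protocol then asks whether she relapsed before 6 weeks postpartum. The rule, not the woman, creates the gap.

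This is a matter of conduct. An analysis plan can choose a denominator or a missing-data convention, but it cannot supply outcomes that nobody collected. The loss may also be informative, since noncompliance could be related to mood, although the documents give no basis for its direction.

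The point is limited to noncompliance removals. Women already lost or who withdraw consent cannot be retained by rule, and women removed at relapse have a known primary outcome.

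**Working it through.** **Is relapse collected after removal anywhere?** The nearest provisions are these.

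- Section 4a, obstetrical and newborn outcomes: chart review of the delivery admission. It does not cover relapse.
- Section 4b: home visits for women who cannot come to the Center. This helps retention but does not follow removed women.
- Section 8b, Psychiatric Urgency/Emergency: participants "sign a release of information form in order to allow study personnel to contact their emergency contact and/or providers if necessary during the study". This sits among the emergency procedures and is limited to the study period.
- The same section keeps psychiatrically ill women who are not at risk of harm in the study. It does not address noncompliance.

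None fills the gap.

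**The plan's own figure.** Inputs from Section 4a: 16 retained, 4 drop-outs among 20. 16 / (1 − 4/20) = 16 / 0.80 = 20, which reproduces the enrollment figure. No alpha, power or test is stated, so there is nothing further to reproduce.

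**Best/worst-case range.** Let x be the relapses among women with known outcomes and m the number with unknown outcomes, with 20 enrolled. The proportion among all 20 lies between x/20 and (x + m)/20, a width of m/20. Each unknown outcome therefore adds 1/20 = 5 points. If fewer than 20 enroll, the step is correspondingly larger.

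The all-20 proportion is below 30% when total relapses are 5 or fewer. It is undecided when x ≤ 5 and x + m ≥ 6:

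| Unknown (m) | Known (n) | Width | Undecided x |
|---|---|---|---|
| 1 | 19 | 5 points | 5 |
| 2 | 18 | 10 points | 4–5 |
| 4 | 16 | 20 points | 2–5 |

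For example, 4/16 (25%) is compatible with 4/20 = 20% to 8/20 = 40%. The last row assigns the whole drop-out allowance to noncompliance and is an upper case. These are bounds, not likelihoods of a wrong reading.

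**Direction against 30%.** With m = 1 or 2, the known-women proportion is below 30% for x ≤ 5 (5/19 = 26.3%, 5/18 = 27.8%). Any change on adding the missing women is from below 30% to 30% or more. With m = 4, changes go both ways: 5/16 = 31.3% becomes 5/20 = 25% if none of the four relapsed.

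**Why the bounds overstate the loss.** Women are seen monthly in pregnancy and at 1, 2, 4 and 6 weeks postpartum, so a removed woman is known to be relapse-free at her last visit. Her remaining risk is 1 − S(end)/S(last visit), where S is the probability of still being relapse-free. This cannot exceed the full-window risk 1 − S(end) if she shares the other women's hazard. As an illustration, assume a full-window risk of 25%, a constant hazard and a last visit at the midpoint: 1 − √0.75 = 1 − 0.866 = 13.4%.

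**Gain in precision.** Exact 95% intervals at an observed 25%: 4/16 gives 7.3% to 52.4% (width 45.1 points); 5/20 gives 8.7% to 49.1% (width 40.4 points). Recovering all four outcomes saves 45.1 − 40.4 = 4.7 points of width.

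**The case against.** The strongest reply is that this is a descriptive pilot. Section 7 specifies tabulations, Section 4a accepts that the design cannot show superiority, and crossing 30% triggers nothing. Sampling error dwarfs the loss. Aim 1 concerns women undergoing the TDM protocol, so a focus on compliant women is defensible. The rule may also bite rarely: Section 10 pays by visit and gives a bonus for a minimum of 5 pregnancy and 2 postpartum visits, and Section 4b offers home visits, which suggests that missed visits alone need not mean removal. All of this stands, and it limits the severity. It does not remove the gap: continued ascertainment keeps both the compliant-women and the all-enrolled readings available, while removal leaves only the first.

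Some stronger readings are tempting but unsupported.

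- A reader might take Section 4g as barring follow-up. It speaks to clinical care, not data collection; the case rests on removal plus silence.
- A reader might apply the Abstract's relapse figure of at least 80% for women who stop mood stabilizers. The documents do not equate noncompliance with stopping lamotrigine and give no relapse rate for noncompliant women.
- A reader might count all 4 drop-outs as noncompliance removals. The allowance must also cover loss to follow-up and withdrawal.
- A reader might infer that the relapse rate will be biased low. The documents do not establish the direction.

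**Conclusion.** The point holds as a modest conduct flaw. As written, Section 4f can leave part of the primary endpoint window unobserved for women who could still be asked, and this cannot be repaired afterwards. With 20 enrolled, the cost is at most 5 percentage points of best/worst-case range per woman, for an unstated number between 0 and 4. That range assumes the drop-out allowance holds. The real loss is smaller, because only the risk after the last visit is unknown.

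The flaw does not invalidate the pilot or its descriptive aim. It merits correction because the data are meant to inform a later randomized trial and the loss is cheap to prevent.

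A separate point, on which this conclusion does not rest: Section 4f removes women at relapse, whereas Section 8b keeps psychiatrically ill women who are not at risk of harm in the study. These passages must be reconciled.

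**What to change.** In Section 4f, distinguish leaving the TDM protocol from leaving outcome follow-up, and state that noncompliance alone does not end relapse ascertainment. Define noncompliance, including whether missed visits count.

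For women who still consent, obtain relapse status to 6 weeks postpartum by phone interview, using the same relapse criteria where possible. Section 8b already envisages phone contact: "If the participant is interviewed by phone and is judged to be at risk, the participant will be instructed". Otherwise obtain it from the treating provider, and extend the release of information to cover this use. Record the source of each outcome, and report the proportion both for all enrolled women and for those who stayed on the TDM protocol. Separately, reconcile Sections 4f and 8b on women who relapse.

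The cost is amended wording, a small consent and release amendment, and a few calls or record requests. The drawback is that SCID-defined episodes are less certain from outside records than hospitalization is, so two standards of ascertainment could mix in one small proportion. Recording the source makes that visible.

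### The primary relapse result is a crude percentage read against <30%, although up to 4 of 20 women may leave before the window closes; a censored estimate with drop-out bounds should stand beside it

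*Protocol*

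**What the plan says.** Protocol Section 7 (and Section 4.a, Data Collection) defines the endpoint: "The primary endpoint is the proportion of women who experience psychiatric relapse from the time of enrollment to 6 weeks postpartum". Section 7 summarises by "percent tabulations for categorical variables" and mentions no time-to-event summary or interval.

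Section 2, Specific Aim 1, sets the reading: "Women undergoing a TDM protocol for lamotrigine will have a low rate (defined as <30%) of psychiatric relapse". Section 7 gives the benchmark: "We do not have a comparison group but would normally expect a relapse rate of approximately 30% based on the literature".

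On numbers, Section 4.a sets a recruitment ceiling of 20. For retention, it plans "with a goal of maintaining a sample size of 16 allowing 4 drop-outs". Section 4.f removes women who are lost to follow-up or noncompliant, and also removes women who meet the relapse criteria. Section 8(b), under psychiatric urgency, keeps in the study a participant who is psychiatrically ill but not at risk of harm. On entry, Section 5 says: "All participants must be in the first 20 weeks of pregnancy at the time of enrollment".

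**The concern.** A proportion over a fixed window is clear only when every woman is followed to the end of it. Here the design tolerates 20% incomplete follow-up (4/20), and the protocol does not say how a woman who leaves without relapse is counted.

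The two obvious percentages err in opposite directions. With all enrolled women in the denominator, a woman lost in mid-pregnancy counts as a success. With only retained women, the relapse-free weeks of those who left are discarded. Women who never relapse have longer in which to drop out, so they are removed more often than relapsers and the percentage rises.

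The downward error favours the study hypothesis. The sponsor intends these data as the basis for a randomised trial, so an error of a few points would carry into its planning.

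**Working it through.** **Inputs.** Up to 20 recruited, goal of 16 retained, 4 drop-outs allowed (Section 4.a). Low means <30% (Aim 1). Window: enrollment to 6 weeks postpartum (Section 7). Entry: first 20 weeks (Section 5).

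**1. The plan's own figure.** 16/(1 − 4/20) = 16/0.80 = 20, which agrees with the stated 20. The protocol gives no alpha, power or alternative rate to reproduce.

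**2. Where the reading changes.** Let x be the observed relapses, with 4 women lost without an observed relapse.

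| x | x/20 | x/16 | (x+4)/20, all drop-outs relapsed |
|---|---|---|---|
| 2 | 10.0% | 12.5% | 30.0% |
| 3 | 15.0% | 18.75% | 35.0% |
| 4 | 20.0% | 25.0% | 40.0% |
| 5 | 25.0% | 31.25% | 45.0% |
| 6 | 30.0% | 37.5% | 50.0% |

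Between 20 and 16 only x = 5 changes sides of <30%. If all drop-outs are taken as relapsed, the reading fails from x = 2 upward.

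**3. How likely x = 5 is.** Assume 16 retained women, each with risk p, so P(X = 5) = C(16,5) p^5 (1−p)^11. This is 0.12, 0.18, 0.21 and 0.20 at p = 20%, 25%, 30% and 35%. At p = 30%, P(X ≤ 4) = 0.45, the chance of reading low over 16. P(X ≤ 5) = 0.66 is the chance over 20. The difference, 0.21, is P(X = 5).

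**4. Average bias.** The model in step 3 fixes who is retained. A simulation lets drop-out and relapse compete in time. Assumptions: 20 women, entry uniform over weeks 6 to 20, delivery at week 40, constant relapse hazard, about 4 drop-outs unrelated to relapse. At a true risk of 30.1%:

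- relapses over all 20: 26.4% (26.4 − 30.1 = −3.7 points)
- relapses over non-drop-outs: 33.3% (33.3 − 30.1 = +3.2 points)
- Kaplan-Meier: 30.0%

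**5. What Kaplan-Meier gives at x = 5.** If all 4 leave after the last relapse, the estimate is 5/20 = 25.0%. If all leave before the first, it is 5/16 = 31.25%. Actual timing places it between.

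**6. Precision.** Exact 95% intervals are 8.7% to 49.1% for 5/20 and 11.0% to 58.7% for 5/16.

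**7. Entry week.** With delivery at week 40, entry at week 6 gives 40 − 6 + 6 = 40 weeks at risk, and entry at week 20 gives 26. Take a constant hazard that gives 30% for entry at week 13 (33 weeks). The risks are then 1 − 0.7^(40/33) = 35.1% and 1 − 0.7^(26/33) = 24.5%. If instead half the cumulative hazard falls postpartum, which all women share, the risks are about 33% and 27%.

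**The case against.** The strongest reply is one of scope. Analysis sets and missing-data rules commonly sit in a SAP, which is not at hand. The protocol also never names 20 and 16 as rival denominators: one is a recruitment ceiling, the other a retention goal. That stands, so silence about the denominator is not the point in itself. The point is that the protocol itself fixes a crude proportion and a 30% line while allowing 20% loss.

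A reader might infer more than the documents support:

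- **That the plan forecasts 4 drop-outs.** It allows for them. The sizes above apply if the allowance is used.
- **That the reading is unstable over many counts.** Between 20 and 16 it changes at one count, and the intervals in step 6 are far wider than the 6.25-point gap.
- **That a decision or error rate is compromised.** Section 7 is descriptive, and Section 4.a says the design will not show superiority.
- **That Kaplan-Meier steadies the <30% reading.** It does not. In a comparable simulation, measured against full follow-up of the same women, it fell on the wrong side of 30% in 12.4% of trials, against 14.6% over all 20 and 11.5% over non-drop-outs.
- **That Kaplan-Meier is always the least biased.** If women bound to relapse leave at three times the rate (an assumption), it averages 25.8% against a true 29.9%, and non-drop-outs give 28.4%. Removal for noncompliance makes such a link possible. This is why bounds are needed and why the percentage should not be dropped.
- **That varying entry week is part of the same defect.** It does not alter the denominator. A Kaplan-Meier curve that keeps completers at risk to the end of the window does not correct for it, and its size depends on the assumed hazard shape.

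**Conclusion.** The point holds as a matter of estimation. If about 4 of 20 women leave for reasons unrelated to relapse, the two crude percentages are off by roughly 3 to 4 points in opposite directions at a true risk of 30%. The all-enrolled figure errs in favour of the hypothesis. A censored estimate removes that average bias under the same assumption, but not if drop-out is related to relapse. The effect on the <30% reading is narrow: one count, with probability about 0.2 at a 30% risk.

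The protocol should add the censored estimate, its interval and the drop-out bounds. The evidence does not support discarding the percentage. Entry week is a separate and smaller limitation.

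**What to change.** In Section 7:

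1. State that all enrolled women are analysed.
2. Report the Kaplan-Meier cumulative risk of first relapse by 6 weeks postpartum with a 95% CI. Censor women lost without relapse at their last assessment, and keep women who complete the window at risk to its end.
3. Keep the simple percentage of all enrolled women beside it.
4. Show the two bounds: all drop-outs well, and all drop-outs relapsed.
5. Report entry week and woman-weeks at risk descriptively.

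Section 4.f (removal at relapse) and Section 8(b) (an ill participant remains in the study) must be reconciled, so that a relapse is never counted as a drop-out and it is clear whether the 16 to be retained include women who relapsed.

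The cost is a few sentences and no new visits. The protocol does not say that dates of relapse and last assessment are recorded, so that should be added. The interval will be wider than for a raw percentage of 20, and relapse timing will be known only to the visit interval, which is monthly in pregnancy.
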